12.2.7. Last on-treatment result

Derived per parameter separately, for values as well as abnormalities.

Three last on-treatment determinations will be done, depending on the chapter of analysis:

1. Including all nonmissing post-baseline values, including “use=No” and unscheduled measurements, up to and including the Week 12 value.
2. Including all nonmissing post-Week 12 values, including “use=No” and unscheduled measurements, up to and including the Week 24 value.
3. Including all nonmissing post-baseline values, including “use=No” and unscheduled measurements, up to and including the Week 24 value.

Early discontinuation visits are considered as on-treatment visits as well.

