After becoming aware of any of the above described abnormal laboratory changes occurring at any one time, an unscheduled visit (i.e. second sequential) must occur to retest within 3 to 5 days.  In each case, there is a need for additional investigations, such as review of ethanol, recreational drug and dietary supplement consumption; testing for acute hepatitis A, B or C infection and biliary tract imaging should be promptly discussed with the Study Medical Monitor.

 At the time of study completion or discontinuation, if a patient should exhibit elevations in serum creatinine  $\geq 33\%$  above the average of screening and baseline values, they should be re-tested every 1 to 2 weeks until the serum creatinine elevation is fully reversed to within 10% of the average of screening and baseline values.

 In each case, hormones in male subjects should be monitored monthly and if no positive dynamics is seen after 3 months from stopping GLPG0634, referral to an andrologist should be considered.

Subjects who stop study medication for any reason will not be replaced. Subjects withdrawing from the study will be encouraged to complete the same final evaluations as subjects completing the study according to the protocol, particularly safety evaluations in the subject's interest, so that data can be recorded in the same way as for subjects who completed the study. Subjects are free to withdraw from the study at any time without providing reason(s) for withdrawal and without prejudice to further treatment. The reason(s) for withdrawal will be documented in the electronic case report form (eCRF).

Reasonable efforts will be made to contact subjects who are lost to follow-up. These must be documented in the subject's file.

The sponsor has the right to terminate the study at any time in case of safety concerns or if special circumstances concerning the study medication or the company itself occur, making further treatment of subjects impossible. In this event, the investigator(s) and relevant authorities will be informed of the reason for study termination.

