3.3. ALGORITHM OF ALLOCATING VISITS TO TIME WINDOWS

All visits (including early discontinuation visits and unscheduled visits but excluding visits without data) will be placed into time windows according to their relative day (DY) in the study, according to the following allocation table:

Time point label	Target day	Interval lower bound	Interval upper bound
Screening (3)	NA	NA	NA
Baseline (1)	NA	NA	NA
Week 1	8	2	11
Week 2	15	12	21
Week 4	29	22	42
Week 8	57	43	70
Week 12	85	71	98
Week 16	113	99	126
Week 20	141	127	154
Week 24	169	155	182
>Week 24 (2)	NA	183	+∞
Follow-up (3)	7-10 days after last visit	NA	NA

(NA = not applicable).

Notes:

- (1) The actual baseline reference value will be determined per parameter as the last available pre-dosing data point, so might differ from this “baseline” visit interval. There will be only one baseline time point in this study: the last nonmissing value prior to first dosing of study drug.
- (2) Visits falling really late in the study (relative day > 182; excluding the follow-up visit) will be allocated to a “>Week 24” interval, and will not be shown in tables nor figures, but will only be listed.
- (3) For the screening and follow-up visits, no time window is defined. The visit as recorded in the eCRF will be used. Follow-up visits of subjects who discontinue the study prior to the Week 12 re-randomization will be shown separately as well in the tables that present the first part of the study only. For tables that present the study as a whole, all follow-up visits will be shown.

Tables, figures and listings will present the time points, not the visits.

For ECGs, a different method will be used. See section 12.3 for the details.

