Shift table per lab test category (hematology, biochemistry, endocrine, urinalysis), lab test, treatment group and time point. The table will present the shift in abnormality (L/N/...) at worst-case and last on-treatment (other time points: not needed) versus the baseline abnormality (L/N/H). Tests without normal ranges will not be presented in this table.

Population: safety.

Table 14.3.2.5: Laboratory data up to Week 12: Treatment-emergent lab abnormalities per time point

Frequency table of the treatment-emergent lab abnormalities per lab test category (hematology, biochemistry, endocrine, urinalysis), lab test, treatment group and time point (including the worst-case). A post-baseline abnormality is considered treatment-emergent if it differs from the baseline result. Tests without normal ranges will not be presented in this table.

Population: safety.

Table to be created for the Week 12 interim analysis as well.

Table 14.3.2.6: Laboratory data up to Week 12: Frequency table of the CTCAE toxicity grades per time point

Frequency table (with cumulative percentages) per lab test category (hematology, biochemistry, endocrine, urinalysis), lab test, treatment group and time point.

Table for selected tests only.

Population: safety.

Table to be created for the Week 12 interim analysis as well.

Table 14.3.2.7: Laboratory data up to Week 12: Shift table of the CTCAE toxicity grades per time point

Shift table per lab test category (hematology, biochemistry, endocrine, urinalysis), lab test, treatment group and time point. The table will present the shift in CTCAE tox grade (0/1/2/3/4) at worst-case and last on-treatment (other time points: not needed) versus the baseline grade (0/1/2/3/4).

Table for selected tests only.

Population: safety.

Table 14.3.2.8: Laboratory data up to Week 12: Treatment-emergent CTCAE toxicity grades per time point

Frequency table of the treatment-emergent lab CTCAE tox grades per lab test category (hematology, biochemistry), lab test, treatment group and time point (including worst-case). A

post-baseline grade is considered treatment-emergent if it is higher than the baseline tox grade.

Table for selected tests only.

Population: safety.

Table to be created for the Week 12 interim analysis as well.

Table 14.3.2.9: Laboratory data up to Week 12: Frequency table of the ATP III classes per time point

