12.4.4. Last on-treatment result

Derived per parameter separately, for values as well as abnormalities.

Three last on-treatment determinations will be done, depending on the chapter of analysis:

1. Including all nonmissing post-baseline values, including “use=No” and unscheduled measurements, up to and including the Week 12 value.
2. Including all nonmissing post-Week 12 values, including “use=No” and unscheduled measurements, up to and including the Week 24 value.
3. Including all nonmissing post-baseline values, including “use=No” and unscheduled measurements, up to and including the Week 24 value.

Early discontinuation visits are considered as on-treatment visits as well.

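### SAP 12.2.7 and 12.4.4 define the last on-treatment result without a last-dose cut-off, so off-drug retests in early stoppers can be reported as on-treatment

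*SAP*

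**What the plan says.** **The rule.** SAP 12.2.7 makes three determinations: to Week 12, after Week 12 to Week 24, and to Week 24 overall. The first admits every nonmissing post-baseline value, including those flagged use=No "and unscheduled measurements, up to and including the Week 12 value". The section adds: "Early discontinuation visits are considered as on-treatment visits as well". SAP 12.4.4 has the same structure for vital signs ("Three last on-treatment determinations will be done, depending on the chapter of analysis"). The date of last dose appears in neither section.

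**Where the values go.** SAP 3.3 says: "All visits (including early discontinuation visits and unscheduled visits but excluding visits without data) will be placed into time windows". The windows are study-day ranges. Screening and follow-up visits are not windowed and keep their eCRF label.

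**Where the result is used.** The laboratory shift tables in SAP 12.2.9 show categories only "at worst-case and last on-treatment (other time points: not needed) versus the baseline abnormality". The descriptive tables of values, changes and percent changes also carry a last on-treatment row.

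**Off-drug measurements in the protocol.** Under Protocol 8.3.4, subjects whose creatinine is at least 33% above the screening/baseline average at completion or discontinuation are to be "re-tested every 1 to 2 weeks until the serum creatinine elevation is fully reversed to within 10% of the average". After a stop under the male-hormone rule, "hormones in male subjects should be monitored monthly and if no positive dynamics is seen after 3 months from stopping GLPG0634", referral is to be considered. Protocol 8.7.1.4.1.3 asks for repeat laboratory tests after an SAE until values are normal, explained or stable.

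**The concern.** The label says on-treatment, but the derivation does not. A subject who stops early and is retested off drug has later nonmissing post-baseline values, and the rule takes the latest. The subjects concerned are largely those stopped for, or left with, a laboratory change.

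For creatinine the direction is predictable. Retesting continues until the value has returned to within 10% of the reference, so the final retest tends to be the recovered one. The last on-treatment row then understates the change at the end of exposure, and more so in an arm with more such stops. Post-SAE laboratory tests are less clear-cut, because they may also end when a value is merely explained or stable. The hormone monitoring has no stated end on recovery.

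At stake are one of the two columns in each laboratory shift table, the last on-treatment rows of the descriptive tables, and some scheduled-week cells. For creatinine change and percent change, last on-treatment is the only end-of-exposure summary, because SAP 12.2.8 derives worst-case for abnormalities only.

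**Working it through.** The plan states no figure on this point, so there is none to reproduce. The check applies the SAP windows to the protocol's retest intervals.

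**Inputs**
- SAP 3.3 windows: Week 4 = Days 22-42, Week 8 = 43-70, Week 12 = 71-98, Week 16 = 99-126, Week 20 = 127-154, Week 24 = 155-182. The targets for Weeks 8 and 12 are Days 57 and 85.
- Protocol 8.3.4: creatinine retests every 7 or 14 days; hormones monthly, taken as 30 days.
- Stop days are illustrative, because the documents give none.

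**Step 1: how many off-drug retests qualify.** Number = floor((cap - stop day) / interval). Days off drug at the latest one = number x interval. Counts are maxima, since creatinine retesting ends on recovery.

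| Stop | Cap | Creatinine, 7-day | Creatinine, 14-day | Hormones, 30-day |
|---|---|---|---|---|
| Day 15 | 98 | 11, latest Day 92 (77 days off) | 5, Day 85 (70) | 2, Day 75 (60) |
| Day 29 | 98 | 9, Day 92 (63) | 4, Day 85 (56) | 2, Day 89 (60) |
| Day 57 | 98 | 5, Day 92 (35) | 2, Day 85 (28) | 1, Day 87 (30) |
| Day 113 | 182 | 9, Day 176 (63) | 4, Day 169 (56) | 2, Day 173 (60) |

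For example, (98 - 29)/7 = 9.86, giving 9 retests, and 9 x 7 = 63 days. The cap here is the end of the window. If the cap is instead the selected Week 12 value (Day 85), the 7-day schedule from Day 29 gives (85 - 29)/7 = 8 retests, the latest 56 days off drug. The conclusion does not change.

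**Step 2: scheduled-week cells.** From a Day 29 stop, both creatinine schedules include Days 57 and 85. These lie exactly on target, so SAP 3.4 selects them for Weeks 8 and 12.

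**Step 3: period 2 rows.** A man who stops on Day 57 and has monthly hormone tests has values on Days 87, 117 and 147 (Weeks 12, 16 and 20). The last two are 60 and 90 days off drug and meet the wording of the second determination in 12.2.7.

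**Step 4: effect on an arm mean.** Take 70 subjects per arm (Protocol 8.8.2), all contributing, and a recovered value of +10%, the upper edge of the recovery range. One subject then moves the arm's mean last on-treatment percent change by:
- (33 - 10)/70 = 0.33 percentage points at the retest trigger;
- (50 - 10)/70 = 0.57 at the stopping threshold;
- (60 - 10)/70 = 0.71 for a +60% rise.

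This treats the SAP baseline as equal to the screening/baseline average.

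**Step 5: when worst-case does not flag the event.** The creatinine stopping rule is relative (more than 50%, twice in sequence). The normal-range and CTCAE scores in SAP 12.2.5 are anchored to ULN. A 50% rise stays at or below ULN if baseline is no more than 1/1.5 = 0.667 x ULN. With baseline 0.60 x ULN, a 60% rise gives 0.60 x 1.60 = 0.96 x ULN: normal, Grade 0.

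**Step 6: completers.** For last dose around Day 169, (182 - 169)/14 = 0.93 gives no retest and (182 - 169)/7 = 1.86 gives at most one (Day 176). Even that one counts only if the cap is read as the whole window; if it is the Week 24 value, none qualifies.

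**The case against.** The strongest reply is that little is lost. A reader might infer that the rule hides the abnormality that caused the stop. The documents do not support that:
- Worst-case (SAP 12.2.8) covers every post-baseline value, including unscheduled and use=No values, and stands beside last on-treatment in the shift tables.
- It also appears in the treatment-emergent tables. For inhibin B and testosterone, Table 14.3.2.12 shows the lowest post-baseline value.
- Adverse events leading to discontinuation or flagged as a stopping criterion have their own tables and require narratives, and all laboratory data are listed.
- If the first of the two raised values fell at a scheduled visit, that week's row normally carries it.

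All of this stands. It leaves the within-range creatinine rise of Step 5.

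The scope is also narrower than the section headings suggest. The protocol requires no off-drug vital-sign retests, so 12.4.4 shares only the missing cut-off and the early-discontinuation rule. For blood counts and liver tests, the 3-5 day retest confirms the finding that triggers the stop; only post-SAE follow-up adds off-drug values. The hormone footnote sets a review at 3 months, not a minimum duration of testing.

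On Step 3, SAP 2.4.1 gives a subject known to have taken no period 2 drug only a part 1 in the analysis. That sentence is written for subjects who passed Week 12. Its logic extends to earlier stoppers, but 12.2.7 does not say so, whereas 12.2.8 does condition on period 2 participation when placing follow-up values.

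Finally, withdrawn subjects have an early discontinuation visit and a follow-up visit 7 to 10 days later, and nothing says that later monitoring is entered as unscheduled visits. That is a fair limit on confidence. The tables are descriptive, without p-values.

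**Conclusion.** The point holds as a labelling and derivation defect. As written, the last on-treatment rule can return values taken weeks after the last dose in early stoppers, and the same values can fill scheduled-week cells. For creatinine the bias is towards no effect, by roughly 0.3 to 0.7 percentage points of an arm's mean per affected subject under the assumptions of Step 4. The one place where the tables may fail to flag the event is a relative creatinine rise within the normal range.

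It does not follow that safety signals disappear from the report, that vital signs are contaminated by required retests, or that Week 24 completers are materially affected.

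The conclusion assumes that the retests are in the trial database as unscheduled visits. The number of subjects affected cannot be derived from the documents. The primary efficacy analysis is untouched. The SAP already uses last dose to bound adverse-event periods (3.2) and to define post-treatment therapies (7.7.1), so the omission for laboratory and vital-sign data is easily put right.

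**What to change.** In SAP 12.2.7 and 12.4.4, keep the Week 12 and Week 24 caps and add a condition: the measurement must be dated no later than the last dose date of the relevant period plus a prespecified margin.

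The sponsor should justify the margin for parent and metabolite. The parent half-life of 5 to 11 h (Protocol 6.7) gives 5 x 11 = 55 h for five half-lives. Protocol 6.2, however, reports higher exposure for the active metabolite, and the readable text gives no half-life for it. A margin of, say, 3 days based on the parent alone is therefore not supported. It could also drop the 3-5 day confirmatory retest if dosing was interrupted meanwhile. The margin should be long enough to keep that retest and a prompt early discontinuation visit. If it reaches 7 days, it can readmit the first weekly creatinine retest.

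Also state that a subject with no period 2 dosing has no period 2 last on-treatment value, and show later retests in a separate post-treatment row, where reversibility can be read. These are analysis definitions only and change no retest or stopping rule.

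Cost: SAP wording, one date condition on a date that SAP 7.8.1 already uses, and one extra table row. A few subjects with a late discontinuation visit will have an earlier value as their last on-treatment result.

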12.2.8. Worst-Case Abnormality

Derived per parameter separately, for abnormalities only.

Three worst-case determinations will be done, depending on the chapter of analysis:

1. Including all nonmissing post-baseline values, including “use=No” and unscheduled measurements, up to and including the Week 12 value. Also including the follow-up value in case the subject did not participate in the second period of the study. If the subject participated in the second period of the study, then the follow-up value will be included in the worst-case of the second period of the study, not of the first period.
2. Including all nonmissing post-Week 12 values, including “use=No” and unscheduled measurements, up to and including the follow-up value.
3. Including all nonmissing post-baseline values, including “use=No” and unscheduled measurements, up to and including the follow-up value.

12.2.8.1. According to normal ranges

Possible categories:

- H = abnormally high: at least one postdose measurement is above the normal range, and there are no values below the normal range.
- L = abnormally low: at least one postdose measurement is below the normal range, and there are no values above the normal range.
- H+L = abnormally high and low: at least one postdose measurement is above the normal range, and at least one other postdose measurement is below the normal range.
- N = normal: all postdose measurements are within normal limits.

12.2.8.2. According to CTCAE tox grades

The worst-case is the highest post-baseline tox grade.

12.2.8.3. According to the ATP III classifications

The worst-case is the highest post-baseline class for LDL, total cholesterol and triglycerides.
The worst-case is the lowest post-baseline class for HDL.

12.2.9. Tables up to Week 12

No formal inferential statistics (p-values) will be derived. Time points to present: screening, baseline, Weeks 1-2-4-8-12, last on-treatment, worst case.

If the subject did not participate in the second period of the study, then the follow-up visit will be presented in the table of the first period of the study. If the subject participated in the second period of the study, then the follow-up value will be presented in the table of the second period of the study, not of the first period.

Table 14.3.2.1: Laboratory data up to Week 12: Descriptive statistics of the actual values per time point

Descriptive statistics of actual values per lab test category (hematology, biochemistry, endocrine, urinalysis), lab test and unit, treatment group and time point.

Population: safety.

Population: safety, selecting subjects with a baseline value within normal range (for endocrine tests only).

Table to be created for the Week 12 interim analysis as well.

Table 14.3.2.2: Laboratory data up to Week 12: Descriptive statistics of the changes from baseline per time point

Descriptive statistics of changes from baseline per lab test category (hematology, biochemistry, endocrine, urinalysis), lab test and unit, treatment group and time point. The actual value at baseline will also be presented in this table.

Population: safety.

Population: safety, selecting subjects with a baseline value within normal range (for endocrine tests only).

Table to be created for the Week 12 interim analysis as well.

Table 14.3.2.3: Laboratory data up to Week 12: Descriptive statistics of the percent changes from baseline per time point

Descriptive statistics of percent changes from baseline per lab test category (hematology, biochemistry, endocrine, urinalysis), lab test and unit, treatment group and time point. The actual value at baseline will also be presented in this table.

Population: safety.

Population: safety, selecting subjects with a baseline value within normal range (for endocrine tests only).

Table to be created for the Week 12 interim analysis as well.

Table 14.3.2.4: Laboratory data up to Week 12: Shift table of the lab abnormalities per time point

Shift table per lab test category (hematology, biochemistry, endocrine, urinalysis), lab test, treatment group and time point. The table will present the shift in abnormality (L/N/...) at worst-case and last on-treatment (other time points: not needed) versus the baseline abnormality (L/N/H). Tests without normal ranges will not be presented in this table.

Population: safety.

Table 14.3.2.5: Laboratory data up to Week 12: Treatment-emergent lab abnormalities per time point

Frequency table of the treatment-emergent lab abnormalities per lab test category (hematology, biochemistry, endocrine, urinalysis), lab test, treatment group and time point (including the worst-case). A post-baseline abnormality is considered treatment-emergent if it differs from the baseline result. Tests without normal ranges will not be presented in this table.

Population: safety.

Table to be created for the Week 12 interim analysis as well.

Table 14.3.2.6: Laboratory data up to Week 12: Frequency table of the CTCAE toxicity grades per time point

Frequency table (with cumulative percentages) per lab test category (hematology, biochemistry, endocrine, urinalysis), lab test, treatment group and time point.

Table for selected tests only.

Population: safety.

Table to be created for the Week 12 interim analysis as well.

Table 14.3.2.7: Laboratory data up to Week 12: Shift table of the CTCAE toxicity grades per time point

Shift table per lab test category (hematology, biochemistry, endocrine, urinalysis), lab test, treatment group and time point. The table will present the shift in CTCAE tox grade (0/1/2/3/4) at worst-case and last on-treatment (other time points: not needed) versus the baseline grade (0/1/2/3/4).

Table for selected tests only.

Population: safety.

Table 14.3.2.8: Laboratory data up to Week 12: Treatment-emergent CTCAE toxicity grades per time point

Frequency table of the treatment-emergent lab CTCAE tox grades per lab test category (hematology, biochemistry), lab test, treatment group and time point (including worst-case). A

post-baseline grade is considered treatment-emergent if it is higher than the baseline tox grade.

Table for selected tests only.

Population: safety.

Table to be created for the Week 12 interim analysis as well.

Table 14.3.2.9: Laboratory data up to Week 12: Frequency table of the ATP III classes per time point

Frequency table (with cumulative percentages) per lab test category (hematology, biochemistry, endocrine, urinalysis), lab test, treatment group and time point.

Table for selected tests only.

Population: safety.

Table to be created for the Week 12 interim analysis as well.

Table 14.3.2.10: Laboratory data up to Week 12: Shift table of the ATP III classes per time point

Shift table per lab test category (hematology, biochemistry, endocrine, urinalysis), lab test, treatment group and time point. The table will present the shift in ATP III class at worst-case and last on-treatment (other time points: not needed) versus the baseline class.

Table for selected tests only.

Population: safety.

Table 14.3.2.11: Laboratory data up to Week 12: Treatment-emergent ATP III classes per time point

Frequency table of the treatment-emergent lab ATP III classes per lab test category (hematology, biochemistry), lab test, treatment group and time point (including worst-case). A post-baseline class is considered treatment-emergent if it differs from the baseline result and is of higher category.

Table for selected tests only.

Population: safety.

Table to be created for the Week 12 interim analysis as well.

Table 14.3.2.12: Laboratory data up to Week 12: Frequency table of percent changes from baseline per time point in inhibin B and testosterone

Frequency table of the percent changes from baseline per lab test category (endocrine), lab test, treatment group and time point. The percent changes from baseline will be categorized

as: <-50%, [-50%,+50%], >+50%. A worst-case will also be shown selected as the lowest post-baseline value.

Table only for inhibin B, free testosterone, total testosterone.

Population: safety – males.

Population: safety, selecting male subjects with a baseline value within normal range.

Table to be created for the Week 12 interim analysis as well.

Table 14.3.2.13: Laboratory data up to Week 12: Shift table of the categorical lab data per time point

Shift table per lab test category (hematology, biochemistry, endocrine, urinalysis), lab test, treatment group and time point. Selecting only the tests with categorical data. The table will present the shift in value at each post-baseline time point versus the baseline value.

Population: safety.

12.2.10. Figures up to Week 12

Figure 14.3.2.1: Laboratory data up to Week 12: Mean plots of the actual values over time

Mean plots of the actual values over time, with each lab test on a new page but with all treatment groups on the same plot using different plot symbols. Unscheduled or follow-up results will not be part of this plot.

Population: safety.

Figure to be created for the Week 12 interim analysis as well.

Figure 14.3.2.2: Laboratory data up to Week 12: Mean plots of the changes from baseline over time

Mean plots of the changes from baseline over time, with each lab test on a new page but with all treatment groups on the same plot using different plot symbols. Unscheduled or follow-up results will not be part of this plot. With a horizontal reference line at zero, indicating no change. Plots will start with a zero mean at baseline.

Population: safety.

Figure to be created for the Week 12 interim analysis as well.

Figure 14.3.2.3: Laboratory data up to Week 12: Mean plots of the percent changes from baseline over time

Mean plots of the percent changes from baseline over time, with each lab test on a new page but with all treatment groups on the same plot using different plot symbols. Unscheduled or follow-up results will not be part of this plot. With a horizontal reference line at zero, indicating no change. Plots will start with a zero mean at baseline.

Population: safety.

Figure to be created for the Week 12 interim analysis as well.

